11.1 Data Sets Analyzed

- All randomized subjects will be included in analysis

11.2 Demographic and Baseline Characteristics

Descriptive statistics will be conducted to assess demographic and baseline characteristics.

11.3 Analysis of Primary Endpoint

The proposed study is a 2 between (groups) x 2 within (pre-post) partial cross-over randomized clinical trial. The primary endpoint of % glucose <120 will be compared between groups for study period 1 using t-tests; within the cross-over group for study period 2 using paired t-tests..

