Primary Objective	To determine if individuals with prediabetes can use GEM plus Libre CGM to improve metabolic control.

Primary Endpoints	Pre-post reduction in percentage of CGM readings > 120 from blinded pre-post LibrePro; additional outcomes of particular interest include, A1C and BG variability
Secondary Objectives	
 (1) To determine if individuals with prediabetes can use the GEM manual with Libre CGM to improve other clinical, psychosocial, and behavioral outcomes. (2) To explore psychological (readiness to change) and physiological (proteomics) measures. (3) To generate user feedback about improving the intervention.
Secondary Endpoints	
 (1) Endpoints will include psychosocial scales, basic demographic information, comparative labs, Steps, Hours Active, or Active Minutes. (2) Analysis of individual proteins and protein pathways measured through use of a multiplex proteomics platform. (3) Endpoint will include the Program Importance Questionnaire
Participation Criteria	
Inclusion Criteria:
 
 • Age 25-70 years • A1C 6.0-6.4 • Documented diagnosis of prediabetes • Have a smart phone • Able to read English, as the GEM guide is currently only available in English • Willing and able to follow the study procedures as instructed 
Exclusion Criteria:
 
 • Diagnosis of diabetes mellitus • Currently taking any diabetes medication • Currently taking medication that promotes insulin resistance or otherwise interferes with metabolic control (e.g. prednisone) • Has a condition that precludes a low carbohydrate diet, such as gastroparesis • Has a physical or medical condition that precludes walking 120 steps per minute, for 10 minutes or longer • Has documented kidney disease that would preclude participation in study per PI discretion • Active or planned cancer treatment. • Extreme visual or hearing impairment that would impair ability to use real-time CGM • Pregnant or anticipates becoming pregnant in the next 4 months. • Anticipates moving within the next 4 months. • Treating physician, for any reason, considers their patient inappropriate for the study (e.g. uncontrolled bipolar disease)
Sample Size	Up to 70 screened participants with prediabetes and an A1c between 6.0-6.4 to provide a cohort of 36 enrolling in the trial, with a goal of at least 30 participants completing the trial.

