4.1 Primary Objective

The primary outcome variable will be participants' pre-post reduction in percentage of CGM readings >120, from blinded pre-post LibrePro. This is most relevant since the goal of GEM is to reduce glucose excursions and since 13% of non-diabetic adults' CGM readings exceed 120.²³

Our hypothesis is that participants assigned to the intervention group will achieve a greater pre-post reduction in percentage of CGM readings >120 than will the control group.

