- Group 2. GEM participants will be given Libre 2 supplies for 4.5 months, an activity monitor and the 4-chapter paper GEM guide which provides: 1) decisive didactic information about the effects of net carbohydrate consumption and routine physical activity on blood glucose fluctuations; 2) instructions to systematically use CGM feedback to educate them about how carbohydrates and physical activity impact their BG excursions, motivate them to repeat choices that lead to lower AUC, activate them to take steps to lower their BG elevations when detected by the high glucose alarm, and investigate the BG impact of new food and activity choices

concerning their effect on their BG; 3) employ structured self-monitoring (diary) to organize and identify personal patterns in their food and physical choices that impact their AUC; 4) GEM Supplement that provides additional information to the manual, e.g. frequently asked questions and answers, nutrient content of low glycemic load foods, case reports, youtube exercise videos; and 5) automated personalized daily text messages to “choose wisely” food and activity choices, and perform daily diary entries. The GEM manual for this prediabetes sample will follow the same format as that used with our diabetes sample: 1) become aware of metabolic costs of routine choices, 2) minimize BG elevations with personally relevant food choices, 3) hasten BG recovery with increased routine physical activity, and 4) plan for continuation of such lifestyle changes. The major adaptation in the GEM Guide for this prediabetes population focused on reducing risk of progression to diabetes and having to initiate diabetes medications. The GEM Guide was adapted based on clinical experience, the qualitative analyses of Yost et al,²⁰ and the literature on secondary prevention.³⁰

Given that this is a pilot study, we did not perform a formal power analysis at this time because there are no data suggesting anticipated change in AUC for adults with prediabetes. However, 20 participants completing the GEM path through the study will provide data to estimate this effect size and therefore to enable power analysis for an anticipated follow-up NIH application. Additionally, N=15 was sufficient to find a pre-post effect in a previous study evaluating a different intervention in a prediabetes population.²⁰

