5.2.2 Primary Endpoint

- pre-post reduction in percentage of CGM readings >120, from blinded pre-post LibrePro.

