11 STATISTICAL METHODS AND CONSIDERATIONS

The primary analyses will be a 2 (group) X 1 (change pre to post assessment) analysis of covariance analyzing change variables, with baseline variables serving as co-variants. The Benjamini-Hochberg procedure³¹ will be employed to control for multiple comparisons. Exploratory correlational analyses will be performed to determine significance of baseline and change variable relationship to primary outcome variable. Analyses will be conducted in SAS v. 9.4. Statistical analysis of de-identified data will be completed at the University of Virginia. The University of Virginia has done all statistical analysis for previous GEM studies.

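### Sections 11 and 11.3 specify different tests for the one primary endpoint (baseline-adjusted ANCOVA versus unadjusted t-test), and nothing says which decides the period-1 comparison

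*Combined protocol and SAP*

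**What the plan says.** All references are to the combined protocol and SAP.

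- **Endpoint.** Section 5.2.2 defines it as "pre-post reduction in percentage of CGM readings >120, from blinded pre-post LibrePro". The hypothesis in Section 4.1 is that the intervention group "will achieve a greater pre-post reduction in percentage of CGM readings >120 than will the control group". Both describe a change score with the threshold above 120.
- **First analysis.** Section 11 describes the primary analyses as an "analysis of covariance analyzing change variables, with baseline variables serving as co-variants". The covariates are plural and not listed. The same paragraph invokes Benjamini-Hochberg without defining the family.
- **Second analysis.** Section 11.3, the section on the primary endpoint, says "The primary endpoint of % glucose <120 will be compared between groups for study period 1 using t-tests", and adds a further test "within the cross-over group for study period 2 using paired t-tests". No covariate appears, and the scale (change or post value) is not stated.
- **Neighbouring text.** Section 2, in its row for primary endpoints, adds that "additional outcomes of particular interest include, A1C and BG variability"; Section 5.2.3 lists those two outcomes as secondary. Section 11.1 says "All randomized subjects will be included in analysis". Section 5.1 says "Given that this is a pilot study, we did not perform a formal power analysis at this time".

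**The concern.** An ANCOVA with baseline covariates and an unadjusted t-test are different tests. They can give different p-values, and their standard errors differ. The plan ranks neither above the other and calls neither a sensitivity analysis, so two analysts following it faithfully could report different conclusions on the Section 4.1 hypothesis. The unlisted covariates and the unstated scale in Section 11.3 widen that freedom.

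The period-1 between-group comparison is the trial's only randomised answer to its hypothesis. The period-2 paired test has no concurrent control. Section 5.1 also intends the data to support sizing a follow-up study, and a standardised between-group effect depends on which SD is used. At r = 0.5 the same raw difference of 0.8 SD is 0.8/√0.75 = 0.92 on the ANCOVA residual scale but 0.8/√1 = 0.80 on the change scale.

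**Working it through.** **Inputs from the plan.** Section 2 gives 36 enrolled and at least 30 completing; Section 5.1 gives up to 20% attrition. Inflating 30 by 20% gives 30 × 1.2 = 36, the stated figure (dividing instead, 30/0.8 = 37.5, so 38). Section 5.1 starts at 2:1 routine care to GEM and moves to 1:1. Thirty completers are therefore 20 versus 10 under the first ratio and 15 versus 15 under the second; the actual mix lies between.

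**Inputs assumed.** The plan gives no alpha, sidedness, SD, effect size or pre-post correlation. I take two-sided 5%, equal pre and post SDs, a true difference of 0.8 SD, r from 0.3 to 0.9, normal data and one baseline covariate.

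**Variance of the treatment effect**, in units of the outcome variance:

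- ANCOVA: 1 − r²
- t-test on change: 2(1 − r)
- t-test on post value: 1

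The ratio of change to ANCOVA is 2(1 − r)/(1 − r²) = 2/(1 + r). For example, at r = 0.5 it is 2/1.5 = 1.33. Estimating one covariate slope with N = 30 inflates the ANCOVA variance by about 1 + 1/26, so that ratio becomes 1.333/1.038 = 1.28.

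**Simulation**, 40,000 trials per setting, 15 versus 15. Disagreement means that one test has p < 0.05 and the other does not.

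| r | Variance ratio, change/ANCOVA | Same, N = 30 | Power, ANCOVA / change | Disagreement at 0.8 SD | Type I error, better of the two |
|---|---|---|---|---|---|
| 0.3 | 1.54 | 1.48 | 58.2% / 42.9% | 24.1% | 7.6% |
| 0.5 | 1.33 | 1.28 | 67.0% / 56.2% | 18.6% | 7.4% |
| 0.7 | 1.18 | 1.13 | 82.5% / 78.0% | 10.0% | 6.8% |
| 0.8 | 1.11 | 1.07 | 93.0% / 91.6% | 4.2% | 6.4% |
| 0.9 | 1.05 | 1.01 | 99.7% / 99.8% | 0.2% | 6.1% |

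Each test used alone held its level (4.8% to 5.1%). At 20 versus 10 the picture is similar: disagreement of 23.4%, 18.7%, 11.4%, 5.1% and 0.5%, and type I error for the better of the two of 6.2% to 7.8%.

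**If a post-value t-test is also admitted**, the best of three has type I error of 9.1% to 10.1% at 15 versus 15. The variance of the post-value test relative to ANCOVA is 1/(1 − r²): 1.10, 1.33, 1.96, 2.78 and 5.26 down the same values of r.

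**Direction of the threshold.** Apart from readings of exactly 120, % <120 equals 100 minus % >120. The t statistic changes sign and the p-value does not; a numerical check gave t = −0.180 and +0.180, both with p = 0.859.

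**Change or post value within ANCOVA.** Subtracting baseline from the outcome only lowers the baseline slope by one. The arm coefficient, its standard error and its p-value are identical.

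**The case against.** The strongest reply is that this is a feasibility pilot without a power analysis, so no stated sample size rests on either test. That is correct, and it limits the harm to the period-1 conclusion and to the effect estimate carried forward. It does not remove the contradiction, because Section 4.1 still states a between-group hypothesis.

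Several stronger readings are tempting, and the documents do not support them:

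- **That there are three rival primary tests and a 9-10% error rate.** The endpoint is defined as a reduction from baseline, so the natural reading of Section 11.3 is a t-test on change. A post-value test is not excluded in words but is named nowhere. The supportable figure is about 6-8%.
- **That the test is chosen after the data are seen.** The plan leaves the choice open; nothing shows when or how it was made.
- **That precision is lost outright.** It is lost only if the t-test is used, and against change scores the loss almost vanishes by r = 0.9. Section 7.1.1 also reports no influence of baseline metrics on outcome in previous studies, very high A1c aside. If that held here for change scores, adjustment would gain little.
- **That the reversed threshold creates a different endpoint.** It is a labelling and direction error that leaves the p-value essentially unchanged.
- **That Section 11.1 favours one method.** A change-score ANCOVA omits a participant without a post window just as a t-test does.
- **That Benjamini-Hochberg would penalise the primary test for A1C and glucose variability.** The family is undefined, so this is conjecture. It is a secondary point, worth settling in the same edit.

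**Conclusion.** The contradiction is real and visible on the page: two tests, one endpoint, no ranking, an unstated scale and a reversed threshold label in the section that should settle the matter. For about 30 completers, under the assumptions listed, the two natural candidates disagree on significance in roughly 10% to 24% of trials for r between 0.3 and 0.7, falling below 1% at r = 0.9. Reporting the better of them would raise type I error from 5% to about 6-8%. Using the t-test on change would cost a variance factor of 1.54 at r = 0.3, declining to 1.05 at r = 0.9. The sizes depend on an unknown correlation; the conflict does not. It should be resolved before the period-1 data are analysed.

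**What to change.** Make Sections 11 and 11.3 state the same single primary analysis. Suggested text:

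> The primary analysis compares the randomised arms in period 1 on the percentage of blinded Libre Pro readings >120, by analysis of covariance with arm, baseline percentage >120 and randomisation phase (2:1 or 1:1) as the only terms. Any t-test is supportive.

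The outcome may be written as change or post value, since the arm effect is the same. The phase indicator is there because the allocation ratio changed during the trial, so any drift in outcome between phases would otherwise be mixed with the arm effect.

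In the same edit:

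- correct <120 to >120 in Section 11.3;
- label the period-2 paired t-test as supportive;
- state the significance level and sidedness;
- say that this one test is the primary test, and apply Benjamini-Hochberg to the secondary outcomes, including A1C and glucose variability, with the Section 2 row worded to match.

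The cost is a wording amendment, which Section 13.1 makes subject to prior IRB approval, and two degrees of freedom: with 30 completers the residual falls from 28 for a t-test to 27 with baseline and 26 with phase. The figures above include the baseline covariate but not the phase term. No new data or participants are needed.

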11.4 Analysis of Secondary Endpoints

Secondary outcome variables will be analyzed with standardized statistical methods for each variable type used to evaluate individual proteins and protein pathways. Correlations will be examined comparing data obtained from proteomic analyses, clinical measurements, and glucose excursion parameters. Data from participants will be compared to themselves to identify changes as a function of glucose control. Data will also be analyzed for groups of individuals by comparing the means and standard errors of the mean.

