3.3 Proteomics

Measuring plasma proteome changes could further enhance the proposed observations and provide new opportunities for advancing the management of patients with prediabetes.²¹ We also propose to sequentially (before, during crossover, and after treatment) measure and analyze the plasma proteome using SomaScan analyses of ~7,500 proteins on a small sample of heparinized plasma (~2cc). This preliminary analysis will begin to characterize the effects of our treatment approach on inflammatory, oxidative stress, and other plasma proteins and protein pathways that change during the evolution of pre-diabetes to diabetes. This data could suggest further testing of specific biomarkers that could be used in the future to guide or assess treatment strategies to perhaps identify responders and non-responders—a more personalized approach and one that ultimately might provide additional impetus for individuals to monitor their glucose levels using CGM and to adhere to treatments that improve their CGM assessments. A recent article (2021) in E BioMedicine emphasizes the importance of characterizing this patient population using comprehensive proteomic approaches.²² Briefly, the authors discovered that: (a) a broad range of blood-borne proteins are altered at the very early stage of screening-detected T2D patients, and (b) that newly identified protein patterns reflect key metabolic syndrome features such as insulin resistance, fatty liver disease, hyperglycemia, and adiposity as well as other protein pathways associated with diabetes. In addition, and importantly, proteomic changes observed at baseline were significantly attenuated during metabolic improvement associated with metformin treatment. They lauded their proteomic approach for its potential to predict diabetic status with high accuracy from the protein signature and as a way to deliver improved and more individualized health care.

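### For about 7,500 proteins, Section 11.4 names only a mean-and-SEM group comparison, which is not a test, and the plan does not say whether or at what level Benjamini-Hochberg covers them

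*Combined protocol and SAP*

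**What the plan says.** Section 3.3 plans to "measure and analyze the plasma proteome using SomaScan analyses of ~7,500 proteins". Sections 4.2 and 5.2.3 list individual proteins and protein pathways among the secondary objectives and endpoints, with the aim of separating eventual responders from non-responders.

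Section 11.4 is the only place that specifies how these data are analysed. It has four elements:

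- a general statement: "Secondary outcome variables will be analyzed with standardized statistical methods for each variable type used to evaluate individual proteins and protein pathways";
- correlations: "Correlations will be examined comparing data obtained from proteomic analyses, clinical measurements, and glucose excursion parameters";
- within-participant comparison: "Data from participants will be compared to themselves to identify changes as a function of glucose control";
- group comparison: "Data will also be analyzed for groups of individuals by comparing the means and standard errors of the mean".

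None of the four comes with a named test, a threshold, a family of comparisons or a false-discovery level.

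Multiplicity appears once, in the opening paragraph of Section 11. That paragraph begins: "The primary analyses will be a 2 (group) X 1 (change pre to post assessment) analysis of covariance analyzing change variables". It then says that the Benjamini-Hochberg procedure "will be employed to control for multiple comparisons", and goes on to exploratory correlational analyses with the primary outcome. It gives no q and does not list the comparisons covered.

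**The concern.** A screen of this width needs a decision rule fixed in advance. Comparing means and standard errors does not supply one. It produces no p-value, so Benjamini-Hochberg cannot act on that step as written. The correlations do produce p-values, but the plan does not say whether Benjamini-Hochberg is applied to them, over which set, or at what level.

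Section 3.3 says that the results could point to specific biomarkers for further testing. If the rule is left open, the length and reliability of the candidate list depend on a choice that could be made after the data are seen, and follow-up work could be built on chance findings.

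**Working it through.** The plan gives no significance level, false-discovery level or expected false-positive count for the proteins, so there is no figure to reproduce. The check is how far the answer moves across the rules that the text permits.

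**Inputs from the documents.** m = 7,500 proteins (Section 3.3). About 30 completers (Section 2, Sample Size). Allocation was RC:GEM 2:1, later 1:1 (Section 5.1), so 15 v 15 and 10 v 20 are used as the main splits.

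**Assumptions.** All proteins are null, values are normal with equal variance, and each rule below is a candidate that the plan does not itself set.

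**Formula.** Expected false differences = m × per-protein false-positive rate. Correlation between proteins does not change this expectation.

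1. *Uncorrected p<0.05:* 7,500 × 0.05 = 375. At p<0.10: 7,500 × 0.10 = 750.
2. *Non-overlapping mean ± SEM:* the rule is |difference| > SE1 + SE2, so the critical value is (SE1 + SE2)/√(SE1² + SE2²).
   - 15 v 15: critical value √2 = 1.414. The normal rate is 0.1573, giving 1,180. With t on 28 df the rate is 0.1683, giving 1,262. Simulation with sample SEs (200,000 draws) gives 0.172, or 1,290.
   - 10 v 20: critical value 1.394. The normal rate is 0.1634, giving 1,225. Simulation gives 0.1821, or 1,366.
3. *Difference greater than 2 SE of the difference:* about 402-415 at 36 or 30 completers.
4. *Non-overlapping 95% confidence intervals:* simulated rates of 0.0053-0.0067, giving 40-50.
5. *Benjamini-Hochberg at an assumed q = 0.05 over all 7,500:* in 4,000 simulated runs of independent null p-values, the chance of any false finding was 0.0495 and the mean number was 0.053.

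| Rule (all assumed) | Expected false differences of 7,500 |
|---|---|
| Non-overlapping 95% CIs | 40-50 |
| p<0.05, uncorrected | 375 |
| Difference > 2 SE of the difference | 402-415 |
| p<0.10, uncorrected | 750 |
| Non-overlapping mean ± SEM | 1,180-1,366 |
| Benjamini-Hochberg, q = 0.05 | about 0.05 |

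To exceed 1,000, a rule needs a per-protein rate above 1,000/7,500 = 0.133. Under the SEM-overlap rule, the proteins must also be mostly null: 1,000/(7,500 × 0.1573) = 85% with the normal rate, or 1,000/(7,500 × 0.1684) = 79% with the t rate.

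**Correlations.** At uncorrected p<0.05, each clinical or glucose variable correlated with all proteins adds 7,500 × 0.05 = 375 expected false hits.

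**What control costs at n = 30.** The critical correlation is r = t/√(28 + t²). At p = 0.05, t = 2.05 and |r| = 0.36. At the first Benjamini-Hochberg step, p = 0.05/7,500 = 0.0000067, so t = 5.52 and |r| = 0.72. That is the strictest step; the cut-off eases as more proteins pass.

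**The case against.** The strongest reply is that Section 11 already states Benjamini-Hochberg, in the parent of 11.4, and does not limit it to the ANCOVA. With a single primary endpoint in 5.2.2, the procedure must reach further to have any purpose. Section 11.4 also opens with a general method for individual proteins, and its SEM sentence is an addition, not a stated decision rule. Finally, the proteomics is called preliminary and exploratory, in a pilot without a formal power analysis.

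Much of this stands, and it rules out several stronger readings that a reader might infer.

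- *That the plan has no error control.* The documents do not support this. Benjamini-Hochberg is stated; its family and level are not.
- *That over a thousand false proteins are to be expected.* This needs an SEM-overlap rule that appears nowhere in the documents, and nearly all proteins to be null.
- *That none of the protein analyses gives a p-value.* This is true only of the mean-and-SEM step. Correlations give p-values, and the unnamed methods and within-participant comparisons may do so.
- *That repeated samples from one person will be pooled as if independent.* Appendix 1 does schedule repeated proteomics samples, but nothing says they will be pooled, and 11.4 refers to comparing participants with themselves. No error rate for pooling can be drawn from the documents.

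What the reply does not cure is the gap itself. Even if Benjamini-Hochberg applies throughout, it needs a p-value per protein, a family and a q. Treating 7,500 proteins as their own family, or pooling them with a handful of clinical outcomes, can give different lists, and the text does not choose. An exploratory label lowers the stakes. It does not tell a reader how a protein came to be listed.

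**Conclusion.** The point holds as a defect of specification and method. For about 7,500 proteins, the one group comparison named in 11.4 is not a test, and the scope and level of the multiplicity procedure in Section 11 are undefined for the proteins and their correlations.

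If all proteins are null, the candidate rules give from about 40 to about 1,370 false differences, with 375 under an uncorrected 5% level, against about 0.05 under Benjamini-Hochberg at an assumed q of 0.05. The upper end belongs to an SEM-overlap reading that the plan does not state. The counts rest on the assumed rules, on completer numbers near 30, and, for the Benjamini-Hochberg simulation, on independent p-values.

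The primary conclusion is not affected. What is affected is how protein findings are reported and whether they can be relied on to choose candidates. The plan should be changed, and this can be done before any protein result exists, because Section 2 has all samples analysed together after collection is complete.

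**What to change.** In Section 11.4, replace the mean-and-SEM comparison with the following.

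- **Per-protein test.** For each protein, compare the randomised groups in study period 1 on change adjusted for that protein's baseline. This is the ANCOVA form in the opening of Section 11, for example on the log scale. Section 11.3 names t-tests for the primary endpoint, so 11.4 should state its own model and not rely on a cross-reference.
- **Multiplicity.** Apply Benjamini-Hochberg at a stated q over all proteins as a family of their own.
- **Correlations.** For each clinical or glucose variable, apply Benjamini-Hochberg over the proteins in the same way, using one value per participant.
- **Reporting.** Give estimates with 95% confidence intervals. Keep means and SEMs as description only.

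The same paragraph should say whether the pathway and within-participant comparisons are tested, and in which family, or mark them as descriptive. The log scale and the value of q are choices for the investigators; what matters is that they are fixed in advance.

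The cost is SAP wording and standard software, with no new data. The drawback is real: fewer proteins will be listed, and at about 30 completers only large effects will be called, with |r| near 0.72 needed at the first Benjamini-Hochberg step against 0.36 at the nominal level.
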